5.5. Justification for Dose

Study RHBY is a long-term extension study for patients who have completed Week 52 of any of the following originating studies: RHBV, RHBW, or RHBX. The ixekizumab dose regimens used in Study RHBY (ixekizumab 80 mg Q2W or ixekizumab 80 mg Q4W) are the same as those used in studies RHBV, RHBW, and RHBX.

6. Study Population

Prospective approval of protocol deviations to recruitment and enrollment criteria, also known as protocol waivers or exemptions, are not permitted.

6.1. Inclusion Criteria

The study population for Study RHBY will include patients from any of the originating studies (RHBV, RHBW, or RHBX), and will therefore include patients with rad-axSpA and patients with nonrad-axSpA, with or without prior use of TNF inhibitors.

For most patients, Week 52 of the originating study (RHBV, RHBW, or RHBX) will coincide with Week 0 (Visit 1) for Study RHBY. Study investigator(s) will review patient data from Week 52 in the respective originating study to determine if the patient meets all inclusion and none of the exclusion criteria to qualify for participation in Study RHBY. If, at Week 52 in the originating study, a patient is not able to enter Study RHBY (e.g., due to unresolved safety concerns), investigational product will be temporarily interrupted and the patient will be evaluated in the originating study for up to 12 weeks beyond Week 52 (i.e., Visit 802 in the originating study) to determine whether treatment with investigational product can resume. If, in the opinion of the investigator, restarting ixekizumab does not pose an unacceptable risk, the patient can begin participation in Study RHBY (Visit 1 [Week 0]).

Patients are eligible to be included in the study only if they meet the following criteria:

- [1.] Have completed the final study visit in Study RHBV, RHBW, or RHBX.
(Note: Patients from Study RHBX are not eligible if they permanently discontinued ixekizumab and were receiving a TNF inhibitor).
- [2.] Must agree to use a reliable method of birth control.
 - If the patient is male, the patient must agree to use a reliable method of birth control during the study and for at least 12 weeks following the last dose of investigational product, whichever is longer. Methods of birth control include, but are not limited to, condoms with spermicide and male sterilization.

OR

- If the patient is female and is a woman of childbearing potential who tests negative for pregnancy, the patient must agree to use a reliable method of birth control or remain abstinent during the study and for at least 12 weeks following the last dose of investigational product, whichever is longer. Methods of birth control include, but are not limited to, oral contraceptives, contraceptive patch, injectable or implantable contraceptives, intrauterine device, vaginal ring, or diaphragm with contraceptive gel.

(Note: Where required by regulation, a highly effective method of birth control is required. A highly effective method of birth control is defined as one that results in a low failure rate [that is, <1% per year] when used consistently and correctly, such as male sterilization, oral contraceptives, contraceptive patch, injectable or implantable contraceptives, intrauterine device, or vaginal ring).

OR

- If a female patient is a woman of nonchildbearing potential she is not required to use any method of birth control. Nonchildbearing potential is defined as:

Women who have had surgical sterilization (hysterectomy, bilateral oophorectomy, or tubal ligation).

- or -

Women who are ≥ 60 years of age.

- or -

Women ≥ 40 and <60 years of age who have had a cessation of menses for ≥ 12 months and a follicle stimulating hormone (FSH) test confirming nonchildbearing potential (≥ 40 mIU/mL or ≥ 40 IU/L).

- [3.] Have given written informed consent approved by Lilly or its designee, and the Investigational Review Board (IRB)/Ethical Review Board (ERB) governing the site.

6.2. Exclusion Criteria

Patients will be excluded from study enrollment if they meet any of the following criteria:

- [4.] Have significant uncontrolled cerebro-cardiovascular (e.g., myocardial infarction [MI], unstable angina, unstable arterial hypertension, severe heart failure, or cerebrovascular accident), respiratory, hepatic, renal, gastrointestinal, endocrine, hematologic, neuropsychiatric disorders, or abnormal laboratory values that developed during the originating ixekizumab study (RHBV, RHBW, or RHBX) that, in the opinion of the investigator, pose an unacceptable risk to the patient if investigational product continues to be administered.
- [5.] Have a known hypersensitivity to ixekizumab or any component of this investigational product.
- [6.] Had investigational product permanently discontinued during a previous ixekizumab study.

- [7.] Had temporary investigational product interruption at any time during or at the final study visit of the originating ixekizumab study (RHBV, RHBW, or RHBX) **and**, in the opinion of the investigator, restarting ixekizumab poses an unacceptable risk for the patient's participation in the study.
- [8.] Have any other condition that, in the opinion of the investigator, renders the patient unable to understand the nature, scope, and possible consequences of the study or precludes the patient from following and completing the protocol.
- [9.] Are currently enrolled in any other clinical trial involving an investigational product or any other type of medical research judged not to be scientifically or medically compatible with this study.

6.3. Lifestyle Restrictions

Study participants should be instructed not to donate blood or blood products during the study.

6.4. Screen Failures

Individuals who do not meet the criteria for participation in this study (screen failure) will not be rescreened.

7. Treatments

7.1. Treatments Administered

During the Lead-In Period (Period 1; Week 0 to Week 24), patients will receive active treatment in the form of ixekizumab 80 mg Q2W or ixekizumab 80 mg Q4W (open-label or blinded depending on the previous originating study; [Table RHBY.2](#)).

During the Extension Period, including blinded, randomized withdrawal-retreatment (Period 2; Week 24 to Week 64), patients who do not meet entry criteria for participation in the randomized withdrawal-retreatment period (Group A) will continue to receive uninterrupted ixekizumab 80 mg Q2W or ixekizumab 80 mg Q4W ([Table RHBY.2](#)).

For patients having achieved a state of sustained remission who do meet the criteria for participation in the 40-week double-blind, placebo-controlled, randomized withdrawal-retreatment period (Group B)

- Patients in the ixekizumab 80 mg Q2W treatment group will be re-randomized to either ixekizumab 80 mg Q2W or placebo. Patients who experience a flare (see Section [5.1](#)) will receive ixekizumab 80 mg Q2W.
- Patients in the ixekizumab 80 mg Q4W treatment group will be re-randomized to either ixekizumab 80 mg Q4W or placebo. Patients who experience a flare (see Section [5.1](#)) will receive ixekizumab 80 mg Q4W.

During the Long-Term Extension Period (Period 3; Week 64 to Week 104), patients in Group A will continue their assigned treatment regimen. Patients in Group A receiving ixekizumab 80 mg Q4W may have their dose escalated to ixekizumab 80 mg Q2W if the investigator determines that the patient may benefit from an increase in frequency of dosing to achieve adequate disease control (see Section [7.4](#)).

During the Long-Term Extension Period, patients in Group B will continue the same treatment that they were receiving at the end of Period 2. However, if a patient experiences a flare and meets criteria for retreatment (see Section [5.1](#)), the patient will be retreated with the ixekizumab treatment regimen (ixekizumab 80 mg Q2W or ixekizumab 80 mg Q4W) that he or she was receiving prior to withdrawal to evaluate whether the patient can regain his or her original response. As of Week 64 and during the Long-Term Extension Period, patients in Group B receiving ixekizumab 80 mg Q4W may also have their dose escalated to ixekizumab 80 mg Q2W, if the investigator determines that the patient may benefit from an increase in frequency of dosing to achieve adequate disease control. Escalation to ixekizumab 80 mg Q2W may occur only after the patient has been retreated with the ixekizumab treatment regimen received during Period 1 (ixekizumab 80 mg Q4W) for at least 12 weeks (see Section [7.4](#)).

The investigator or his/her designee is responsible for the following:

- Explaining the correct use of the investigational product to the patient/patient caretaker
- Verifying that instructions are followed properly

- Maintaining accurate records of investigational product dispensing, collection, and administration
- Returning all unused medication to Lilly or its designee at the end of the study

Patients will be instructed to contact the investigator as soon as possible if they have a complaint or problem with the investigational product so that the situation can be assessed.

Further instructions and special considerations for the administration of the investigational product are provided in Sections [7.1.1](#) and [7.1.2](#).

**Table RHY.2. Summary of Treatment Regimens
Study RHY**

Originating Study	Treatment at End of Originating Study	Treatment During RHY Period 1	Treatment During RHY Period 2 and Period 3
RHBV or RHBW	ixekizumab 80 mg Q2W	ixekizumab 80 mg Q2W (open-label) [Dose: 1 ixekizumab 80-mg Q2W injection (beginning at Week 0)]	Group A: open-label ixekizumab 80 mg Q2W [Dose: 1 ixekizumab 80-mg Q2W injection (beginning at Week 24)]
	ixekizumab 80 mg Q4W	ixekizumab 80 mg Q4W (open-label) [Dose: 1 ixekizumab 80-mg Q4W injection (beginning at Week 0)]	Group B: blinded ^{a,d} ixekizumab 80 mg Q2W (blinded) [Dose: 1 ixekizumab 80-mg Q2W injection (beginning at Week 24)] or placebo (blinded) [Dose: 1 placebo for ixekizumab injection Q2W (beginning at Week 24)]

Originating Study	Treatment at End of Originating Study	Treatment During RHBY Period 1	Treatment During RHBY Period 2 and Period 3
RHBX	rescued to ixekizumab 80 mg Q2W	ixekizumab 80 mg Q2W (open-label) [Dose: 1 ixekizumab 80-mg Q2W injection (beginning at Week 0)]	Group A: open-label ixekizumab 80 mg Q2W [Dose: 1 ixekizumab 80-mg Q2W injection (beginning at Week 24)] Group B: blinded ^{a,d} ixekizumab 80 mg Q2W (blinded) [Dose: 1 ixekizumab 80-mg Q2W injection (beginning at Week 24)] or placebo (blinded) [Dose: 1 placebo for ixekizumab injection Q2W (beginning at Week 24)]
	ixekizumab 80 mg Q2W (blinded)	ixekizumab 80 mg Q2W (blinded) ^e [Dose: 1 ixekizumab 80-mg Q2W injection (beginning at Week 0)]	Group A: blinded ^e ixekizumab 80 mg Q2W [Dose: 1 ixekizumab 80-mg Q2W injection (beginning at Week 24)] Group B: blinded ^{a,d,e} ixekizumab 80 mg Q2W (blinded) [Dose: 1 ixekizumab 80-mg Q2W injection (beginning at Week 24)] or placebo (blinded) [Dose: 1 placebo for ixekizumab injection Q2W (beginning at Week 24)]

Originating Study	Treatment at End of Originating Study	Treatment During RHBY Period 1	Treatment During RHBY Period 2 and Period 3
	ixekizumab 80 mg Q4W (blinded)	ixekizumab 80 mg Q4W (blinded) ^e [Dose: 1 ixekizumab 80-mg Q4W injection (beginning at Week 0); and 1 placebo for ixekizumab injection Q4W (beginning at Week 2)]	
Group A: blinded^{c,e} ixekizumab 80 mg Q4W [Dose: 1 ixekizumab 80-mg Q4W injection (beginning at Week 24); and 1 placebo for ixekizumab injection Q4W (beginning at Week 26)]
 
Group B: blinded^{b,d,e} ixekizumab 80 mg Q4W (blinded) [Dose: 1 ixekizumab 80-mg Q4W injection (beginning at Week 24); and 1 placebo for ixekizumab injection Q4W (beginning at Week 26)] or placebo (blinded) [Dose: 1 placebo for ixekizumab injection Q2W (beginning at Week 24)]

	placebo (blinded)	ixekizumab 80 mg Q4W (blinded) ^e [Dose: 1 ixekizumab 80-mg Q4W injection (beginning at Week 0); and 1 placebo for ixekizumab injection Q4W (beginning at Week 2)]	
Group A: blinded^{c,e} ixekizumab 80 mg Q4W [Dose: 1 ixekizumab 80-mg Q4W injection (beginning at Week 24); and 1 placebo for ixekizumab injection Q4W (beginning at Week 26)]
 
Group B: blinded^{b,d,e} ixekizumab 80 mg Q4W (blinded) [Dose: 1 ixekizumab 80-mg Q4W injection (beginning at Week 24); and 1 placebo for ixekizumab injection Q4W (beginning at Week 26)] or placebo (blinded) [Dose: 1 placebo for ixekizumab injection Q2W (beginning at Week 24)]

Abbreviations: Q2W = every 2 weeks; Q4W = every 4 weeks.

- a Patients who experience a flare and meet the criteria for retreatment during Period 2 or Period 3 will receive ixekizumab 80 mg Q2W.
- b Patients who experience a flare and meet the criteria for retreatment during Period 2 or Period 3 will receive ixekizumab 80 mg Q4W. As of Week 64, patients in Group B may have their dose escalated to ixekizumab 80 mg Q2W only after the patient was retreated upon flare with ixekizumab 80 mg Q4W for at least 12 weeks (Section [7.4](#)).
- c As of Week 64, patients in Group A receiving ixekizumab 80 mg Q4W may have their dose escalated to ixekizumab 80 mg Q2W (Section [7.4](#)). Dose escalation may begin at the next scheduled visit or at an unscheduled visit prior to the next scheduled visit.
- d All patients in Group B will remain on blinded study drug from Week 24 until the completion of the study or time of flare (Section [7.3](#)).
- e For patients entering Study RHBY from Study RHBX who were receiving blinded treatment at the end of the originating study, patients will continue to receive blinded treatment in Study RHBY until the 52-week datalock for Study RHBX is achieved.

7.1.1. Administration of Investigational Product

Administration: Injections will be self-administered SC by the patient or caregiver. It is recommended that these injections be administered away from the investigational site. If the patient or caregiver is not able to administer any dose throughout the study, study site staff may administer that injection.

Refer to the appropriate *Manual Syringe Directions for Use* provided by the sponsor for the investigational product. Note that in the case a study drug injection is performed in an arm, it is not to be given in the same arm from which patient blood samples, including PK samples, are drawn at relevant visits.

Study Drug Administration Logs will be dispensed to each patient for recording pertinent data about each injection; details of the use of these logs are provided in Section [7.2.1](#).

Possible injection sites are identified in the *Manual Syringe Directions for Use*. The injection site may be rotated to another area for subsequent doses.

7.1.2. Special Treatment Considerations

All biological agents carry the risk of systemic allergic/hypersensitivity reactions. Clinical manifestations of these reactions may include, but are not limited to:

- skin rash
- pruritus (itching)
- urticaria (hives)
- angioedema (e.g., swelling of the lips and/or tongue)
- anaphylactic reaction

Sometimes these reactions can be life threatening. Proteins may also cause redness, itching, swelling, or pain locally at the injection site; therefore, all patients are to be closely monitored for signs or symptoms that could result from such reactions, educated on the signs or symptoms of these types of reactions, and instructed to contact the study site immediately if any of the symptoms are experienced following an injection. If a patient experiences an acute allergic/hypersensitivity reaction after an injection of investigational product, he or she is to be managed appropriately and given instruction to receive relevant supportive care. Additionally, for an event judged by the investigator to be a potential systemic allergic/hypersensitivity reaction, a blood sample will be drawn as soon as possible for immunogenicity and PK testing (Section [9.4.9](#)).

For patients who experience a potential allergic/hypersensitivity reaction, consideration for any premedication for future injections will be agreed upon between the investigator and sponsor. Examples of potential allergic/hypersensitivity reactions that might merit premedication include mild-to-moderate skin rashes, mild-to-moderate generalized pruritus and/or urticaria, and mild-to-moderate injection site reactions (e.g., injection site erythema, injection site pruritus, etc.). Patients who develop clinically significant systemic allergic/hypersensitivity reactions

following administration of investigational product that do not respond to symptomatic medication or result in clinical sequelae or hospitalization are to be discontinued from study treatment and not receive further doses of investigational product, with or without premedication (see Section 8.1.1). Medications considered appropriate for premedication include, but are not restricted to, acetaminophen/paracetamol up to 1000 mg and antihistamines (e.g., oral diphenhydramine 50 mg) given after all efficacy assessments have been completed for a given visit. Patients may self-premedicate at home prior to administration of investigational product, as directed by the investigator. All such premedications will be recorded as concomitant medications. Corticosteroids are not permitted as agents for premedication.

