8.1. Discontinuation from Study Treatment

8.1.1. Permanent Discontinuation from Study Treatment

The following criteria must be followed for discontinuation from study treatment. Patients will enter into the Post-Treatment Follow-Up Period (Period 4) if they discontinue from study treatment.

- [1] Discontinuation of the investigational product for abnormal liver tests should be considered by the investigator when a patient meets 1 of the following conditions after consultation with the Lilly designated medical monitor:
 - alanine aminotransferase (ALT) or aspartate aminotransferase (AST) >8x upper limit of normal (ULN)
 - ALT or AST >5xULN for more than 2 weeks
 - ALT or AST >3x ULN and total bilirubin level >2xULN or prothrombin time >1.5xULN
 - ALT or AST >3xULN with the appearance of fatigue, nausea, vomiting, right upper-quadrant pain or tenderness, fever, rash, and/or eosinophilia (>5%)
 - alkaline phosphatase >2.5xULN and total bilirubin >2xULN
 - alkaline phosphatase >2.5xULN with the appearance of fatigue, nausea, vomiting, right upper quadrant pain or tenderness, fever, rash, and/or eosinophilia (>5%)
- [2] Other Laboratory tests:
 - neutrophil (segmented) counts (see safety monitoring for neutropenia in Section 9.4.10.1):
 - <500 cells/ μ L (<0.50x10³/ μ L or <0.50 GI/L)

- ≥ 500 and < 1000 cells/ μ L ($\geq 0.50 \times 10^3/\mu$ L and $< 1.00 \times 10^3/\mu$ L or ≥ 0.50 GI/L and < 1.00 GI/L) (based on 2 test results; the second test performed within 1 week from knowledge of the initial result)
- ≥ 1000 and < 1500 cells/ μ L ($\geq 1.00 \times 10^3/\mu$ L and $< 1.50 \times 10^3/\mu$ L or ≥ 1.00 GI/L and < 1.50 GI/L) (based on 3 test results as specified in Section 9.4.10.1)
 - AND - a concurrent infection
- total white blood count (WBC) count < 2000 cells/ μ L ($< 2.00 \times 10^3/\mu$ L or < 2.00 GI/L)
- lymphocyte count < 500 cells/ μ L ($< 0.50 \times 10^3/\mu$ L or < 0.50 GI/L)
- platelet count $< 50,000$ cells/ μ L ($< 50 \times 10^3/\mu$ L or < 50 GI/L)

Note: Laboratory test(s) that may result in discontinuation based on a single result may be repeated once if there is a technical error or clinical reason to believe a result may need to be retested. Laboratory tests can only be repeated after consultation with Lilly medical.

Investigational product should not be administered in these cases until retest result is available.

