- [3] The patient experiences a severe AE, an SAE, or a clinically significant change in a laboratory value that, in the opinion of the investigator, merits the discontinuation of the investigational product and appropriate measures being taken. In this case, Lilly or its designee is to be notified immediately. Refer to AEs, Section 9.2.
- [4] Any positive TB test that indicates TB test conversion since prior testing (based on patient medical history), AND the patient does not receive appropriate treatment for latent TB; or there is evidence of active TB infection at any time.
- [5] Clinically significant systemic hypersensitivity reaction following SC administration of investigational product that does not respond to symptomatic medication or results in clinical sequelae.
- [6] The patient becomes pregnant.
- [7] The patient develops a malignancy.

Note: Patients may be allowed to continue if they develop no more than 2 nonmelanoma skin cancers during the study.

- [8] Enrollment in any other clinical trial involving an investigational product or enrollment in any other type of medical research judged not to be scientifically or medically compatible with this study.

[9] It is recommended that the patient is assessed by a psychiatrist or appropriately trained professional to assist in deciding whether the patient is to be discontinued from the study in the following circumstances:

The patient, at any time during the study, scores a 3 for Item 12 (Thoughts of Death or Suicide) on the Quick Inventory of Depressive Symptomatology-self report (16 items) (QIDS-SR16);

OR

develops active suicidal ideation with some intent to act with or without a specific plan (yes to question 4 or 5 on the “Suicidal Ideation” portion of the Columbia-Suicide Severity Rating Scale [C-SSRS]);

OR

develops suicidal behaviors as recorded on the C-SSRS.

[10] The investigator or attending physician decides that the patient is to be withdrawn from study treatment.

[11] The patient requests to be withdrawn from study treatment.

[12] Lilly or its designee stops the patient’s participation in the study or Lilly stops the study for medical, safety, regulatory, or other reasons consistent with applicable laws, regulations, and good clinical practice (GCP).

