9.2.1. Serious Adverse Events

An SAE is any AE from this study that results in one of the following outcomes:

- death
- initial or prolonged inpatient hospitalization
- a life-threatening experience (i.e., immediate risk of dying)
- persistent or significant disability/incapacity
- congenital anomaly/birth defect
- considered significant by the investigator for any other reason: important medical events that may not result in death, be life-threatening, or require hospitalization may be considered serious, based upon appropriate medical judgment.

Although all AEs occurring after signing the ICF are recorded in the CRF, SAE reporting begins after the patient has signed the ICF and has received investigational product. However, if an SAE occurs after signing the ICF, but prior to receiving investigational product, it needs to be reported ONLY if it is considered reasonably possibly related to study procedure.

Study site personnel must alert Lilly or its designee of any SAE within 24 hours of investigator awareness of the event via a sponsor-approved method. If alerts are issued via telephone, they are to be immediately followed with official notification on study-specific SAE forms. This 24-hour notification requirement refers to the initial SAE information and all follow-up SAE information.

Pregnancy (during maternal or paternal exposure to investigational product) does not meet the definition of an AE. However, to fulfill regulatory requirements any pregnancy should be reported following the SAE process to collect data on the outcome for both mother and fetus.

Investigators are not obligated to actively seek AEs or SAEs in patients once they have discontinued and/or completed the study (the patient summary CRF has been completed). However, if the investigator learns of any SAE, including a death, at any time after a patient has been discharged from the study, and he/she considers the event reasonably possibly related to the study treatment or study participation, the investigator must promptly notify Lilly.

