[D3] In the opinion of investigator, if a patient experiences a severe AE, an SAE, or a clinically significant change in a laboratory value that merits the discontinuation of the investigational product and appropriate measures being taken.	Monitor	From monitor's list
[D4] Any positive TB test and the patient does not receive appropriate treatment for latent TB; or there is evidence of active TB infection at any time	Monitor	From monitor's list.
[D5] Clinically significant systemic hypersensitivity reaction that does not respond to treatment	Monitor	From monitor's list
[D6] Patient became pregnant	Monitor	From monitor's list
[D7] Patient developed a malignancy (Patients may be allowed to continue if they develop no more than 2 nonmelanoma skin cancers during the study)	Monitor	From monitor's list

Important Protocol Deviation Category/Subcategory/Study Specific	Source to Identify Protocol Deviationa	Statistical Programming Guidance for Clinical Study Report
[D8] Enrolled in prohibited medical research	Monitor	From monitor's list
[D12] Lilly stopped the patient participation	Monitor	From monitor's list
[D13] Patient became HBV DNA positive	Monitor/stats	From monitor's list, or stats program based on HBV DNA records.
[D14] Patient has a confirmed diagnosis of PCP during the study for patients from Japan sites	Monitor	From monitor's list
Category: Study Procedures		
Subcategory: Excluded Con-meds	Monitor	Either from monitor's list .
Subcategory: Lab/Imaging Criteria		
Missing lab chemistry and hematology: missing at Week 0, or not having at least 1 visit after Week 0.	Stats	If missing at Week 0 from RHBY, or not having at least 1 visit after Week 0 from RHBY.
Subcategory: Other		
Missing QIDS total score: missing at Week 0 or not having at least one scheduled visit in each period.	Stats	If missing QIDS total score at Week 0 or not having at least one scheduled visit in each period
Missing Columbia scale score at any visit	Monitor and Stats	From monitor's list; if missing Columbia scale at any visit
Incorrect IWRS entries of partial ASDAS scores or CRP resulting in errors to define sustained remission status during Period 1 or the 1st flare at the post-randomization visits during Period 2 and Periods 2 and 3 combined	Monitor	From monitor's list, Stats will use program to support for data checking
Had unqualified site personnel perform clinical safety and/or efficacy assessments	Monitor	From monitor's list

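### The hypersensitivity stopping rule lists hospitalization in Protocol 7.1.2 but not in criterion [5] of the mandatory list in 8.1.1, and SAP deviation row [D5] is narrower than both

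*Protocol*

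**What the plan says.** Three places state when a systemic hypersensitivity reaction ends study treatment, or when failure to end it is a deviation.

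- **Protocol 7.1.2 (Special Treatment Considerations).** Patients with clinically significant systemic reactions "that do not respond to symptomatic medication or result in clinical sequelae or hospitalization are to be discontinued from study treatment". They are to receive no further doses, "with or without premedication (see Section 8.1.1").
- **Protocol 8.1.1 (Permanent Discontinuation from Study Treatment).** The list opens with "The following criteria must be followed for discontinuation from study treatment". Criterion [5] reads: "Clinically significant systemic hypersensitivity reaction following SC administration of investigational product that does not respond to symptomatic medication or results in clinical sequelae". Criterion [3] of the same list covers a severe adverse event, a serious adverse event or a significant laboratory change "that, in the opinion of the investigator, merits the discontinuation of the investigational product".
- **SAP 6.15, Table RHBY.6.11.** Among the violations of the discontinuation criteria, row [D5] reads: "Clinically significant systemic hypersensitivity reaction that does not respond to treatment". Its source is given as the monitor, and its programming guidance is the monitor's list. Row [D3] mirrors criterion [3] and keeps the investigator-opinion condition.

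Protocol 9.2.1 counts "initial or prolonged inpatient hospitalization" among the outcomes that make an adverse event serious.

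**The concern.** Section 7.1.2 points to 8.1.1 for its rule, so a reader expects the two to match, and they do not. Section 8.1.1 is where a site looks when deciding whether treatment must stop. If a trigger appears in 7.1.2 and not there, sites may handle the same event differently depending on which section they consult.

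The SAP row matters for a separate reason. It does not decide who stops. It shapes which failures to stop are recorded as important deviations. If it names fewer triggers than the protocol, a monitor working from its wording could leave continued dosing unrecorded even where both protocol sections required a stop.

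Protocol 3.3 names serious hypersensitivity as an important potential risk, and 9.2.2 lists allergic reactions among the adverse events of special interest. Section 7.1.1 recommends that injections be given away from the site. What is at stake is consistent application of a safety rule and consistent reporting of departures from it.

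**Working it through.** No arithmetic beyond counting applies. The plan states no figure on this point, so the check is a comparison of texts.

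**Triggers named in each place**

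| Trigger | Protocol 7.1.2 | Protocol 8.1.1 [5] | SAP [D5] |
|---|---|---|---|
| Non-response to symptomatic medication | yes | yes | yes, worded as treatment |
| Clinical sequelae | yes | yes | no |
| Hospitalization | yes | no | no |
| Count | 3 | 2 | 1 |

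Relative to 7.1.2, criterion [5] lacks 3 − 2 = 1 trigger and [D5] lacks 3 − 1 = 2. Relative to criterion [5], the criterion whose number it carries, [D5] lacks 2 − 1 = 1.

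**Three test cases, each a clinically significant systemic reaction**

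1. *The reaction does not respond to symptomatic medication.* Both protocol sections require stopping, and [D5] covers continued dosing. There is no conflict.
2. *The reaction responds but leaves sequelae, without hospitalization.* Both protocol sections require stopping. [D5] as worded does not cover continued dosing. This gap remains however the hospitalization question is settled.
3. *The patient is hospitalized, responds, and has no sequelae.* Section 7.1.2 requires stopping. Criterion [5] is not met. Because hospitalization makes the event serious, criterion [3] is reached, but it requires stopping only if the investigator judges that the event merits it. [D5] as worded does not cover continued dosing, and [D3] covers it only under the same judgment.

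**Is this current text?** Yes. In the amendment summary (Protocol Appendix 5), the only revision shown to 8.1.1 concerns criterion [13]. No change is shown to 7.1.2 or to criterion [5].

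**The case against.** Three objections carry weight.

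*No passage permits redosing.* A reader might infer that a hospitalized patient must stop under 7.1.2 but may be redosed under 8.1.1. The documents do not support that. Section 8.1.1 lists conditions for stopping and does not say that a patient who meets none of them may continue. Section 7.1.2 is itself a requirement, and a site that stops such a patient complies with both sections. This stands in full. The fault is a cross-reference that does not carry the whole rule, not a pair of rules that cannot both be obeyed.

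*Other provisions catch the event.* A hospitalized reaction is a serious adverse event, reportable to the sponsor within 24 hours under 9.2.1. Criterion [3] directs the investigator to consider stopping, criteria [10] and [12] let the investigator or sponsor stop treatment, and 7.1.2 has investigator and sponsor agree on premedication for later injections. So the sponsor would know of the event. These routes reduce the risk but do not remove the mismatch, because they put discretion where 7.1.2 states a requirement.

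*[D5] is a label, not a check.* A reader might infer that the SAP runs a deviation check that fails for two triggers, or that continued dosing would go unflagged. The row is completed from the monitor's list and nothing is programmed for it. A monitor who reads the protocol could still record the deviation, and the general definition in SAP 6.15, which includes effects on a subject's safety, leaves room to do so. Other rows are shortened too: [D4] omits the test-conversion condition in criterion [4]. What survives is narrower. With no programmed backstop, the wording is what guides the monitor, and it drops a limb that criterion [5] states. Neighbouring rows keep their conditions: [D2-N] carries its thresholds and the infection condition, and [D7] carries the skin-cancer exception.

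**Conclusion.** The inconsistency is real and limited. Criterion [5] of 8.1.1 omits one of the three triggers in 7.1.2, although 7.1.2 cites 8.1.1. For a hospitalized reaction that resolves without sequelae, a site using only the 8.1.1 list would find investigator discretion where 7.1.2 requires stopping. SAP [D5] as worded names one of the three triggers and omits sequelae, on which the two protocol sections agree.

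The conclusion assumes that the cross-reference means the two protocol sections to state one rule, and that [D5] corresponds to criterion [5], as its number suggests. The documents give no expected count of such events, so their frequency cannot be sized. The primary analysis, power and alpha are unaffected. This is an internal inconsistency in a safety rule and its reporting, and worth correcting because the correction is small.

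**What to change.** Reconcile Protocol 7.1.2, criterion [5] of Protocol 8.1.1 and row [D5] of SAP Table RHBY.6.11 so that one identical set of triggers, in the same words, stands in all three. Which set is right is a clinical decision for the sponsor's medical team, and this review proposes none. The cost is wording in whichever of the three places the decision affects, with no change to data collection or programming.
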